7.3.1.2 Extravasation

Caution should be exercised to avoid para-venous leakage when administering FCM. Para-venous leakage of FCM at the administration site may lead to irritation of the skin and potentially long-lasting brown discoloration at the site of administration. In case of para-venous leakage, the administration of FCM must be stopped immediately and another good venous access must be sought.

7.3.2 Safety issues with Ferrous Sulphate

7.3.2.1 Immune system disorders

Allergic reactions to FS have been reported. Ask patient to report any unusual effect promptly.

7.3.2.2 Gastro-intestinal disorders

Abdominal discomfort and anorexia, abdominal pain, nausea, and vomiting (these are usually dose related), constipation, diarrhea, and dark stools. Contact irritation can occur with ferrous sulphate tablets resulting in erosion or ulceration, particularly if they become lodged in the upper gastrointestinal tract.

Caution:

- Ask patients to keep medication out of the sight and reach of children, as overdose may be fatal.
- Ask about previous allergy to iron formulations.
- Administer oral FS with caution in patients with existing gastrointestinal disease like difficulty in swallowing and inflammatory bowel diseases.
- Due to the risk of mouth ulcerations and tooth discoloration, tablets should not be sucked, chewed, or kept in the mouth but swallowed whole with water.
- Advise to take FS 1 hour before meals or 2 hours after meals with a full glass of water

7.4 Data analysis plan for adverse events (Harm)

Using intention to treat analysis, the absolute risk, the frequency/incident rate and severity grade of anticipated adverse drug reactions such as abdominal pain, nausea and vomiting, hypotension and hypophosphatemia for participants in each study arm, the incident rate of any Serious Adverse Reactions (SAR) which are SAEs that are thought to be causally linked to the trial drug and Suspected Unexpected Serious Adverse Reaction (SUSAR) which are unexpected occurrence of a SAR for each arm of the study will be collated and analyzed. The mean and SDs or median and interquartile range for serum phosphate level will be calculated as appropriate, while extreme values will be stated if observed.

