4.9 Laboratory evaluations

Standard clinical laboratory evaluations will be performed as follows:

- Hemoglobin concentration with the Hemocue haemoglobinometer at screening, two and six weeks and six months postpartum. Complete the *Hb check worksheet* as appropriate (*Appendix i*).
- Malaria rapid diagnostic test (RDT) with SD BIOLINE Malaria Ag P.f at enrollment, two and six weeks
 postpartum and if symptomatic for malaria at any time. Complete the *Malaria POCT worksheet* as
 appropriate (Appendix ii).
- Full blood count at baseline (enrollment), two weeks, six weeks, and six months postpartum. At each visit, 4mls of blood will be collected in an EDTA vacutainer. *Complete blood sample collection log for study visits on REDCap (Appendix iii)*.
- Iron profile: comprises serum iron, serum ferritin, serum transferrin and percentage transferrin saturation will be done at baseline (enrollment), six weeks and six months postpartum. At each visit, 4mls of blood will be collected into a Serum separating tubes (SST) tube. *Complete blood sample collection log for study visits on REDCap*
- Maternal serum phosphate and other biomarkers: The biomarkers of phosphate homeostasis and bone turnover to be measured are Vitamin D, alkaline phosphatase, total procollagen type 1 N-terminal propeptide (P1NP), fibroblast growth factor 23 (FGF23), calcium (Ca) and phosphate (PO4) at baseline (enrollment), 2 weeks (Ca, PO4 and ALP only) and at 6 weeks postpartum. Two (2) SST tubes will be used for sample collection and 4mls of blood will be collected in each tube.
 Complete blood sample collection log for study visits on REDCap.

All samples aside the point of care tests (POCT) will be analyzed at Synlab (an internationally accredited medical laboratory). As a third-party, a contract is in place between the University of Lagos and Synlab. The following steps will be taken at blood sampling:

- Research nurse assistants will collect blood sample as indicated for study visit using an appropriate vacutainer system.
- Complete the *laboratory tests request form* (Appendix iv) with participant's study ID, study site code and visit type (PP-1 to PP-4) to accompany the samples to the lab.
- Document date and time samples were taken and type of test in blood sample collection log on REDCap for study visit.
- Call the dispatch rider for samples pick up within 2-3 hours of sample collection.

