 - Observation/monitoring every 15 min and for 30 min after the infusion finishes.
 - A test dose is not appropriate or necessary as it may give false reassurance.
 - Patients should be closely monitored for signs of hypersensitivity during and for at least 30 min after administration.

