9.3 Data Management and analysis

The assignment of participants into analysis populations will be performed prior to database lock and any data analysis.

- Randomized all participant who receive a randomization number.
- Intention-to-treat (ITT) all randomized patients with at least one relevant post-baseline efficacy assessment, and who had at least one dose of study drug. Following the intention-to-treat principle, patients will be analyzed according to the treatment they were assigned to at randomization.
- Primary Analysis (PA) all ITT patients that completed 2- and 6-weeks postpartum visit.
- Per Protocol (PP) all PP patients that meet all the following:
 - Took at least 80% of scheduled study drug
- Safety all patients that received at least one dose of study drug and had at least one post-baseline safety assessment. Patients will be analyzed according to treatment received.

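### Section 7.4 analyses harms by intention to treat while 9.3 defines an as-treated Safety set; nothing says which governs, and the 9.3 ITT set can omit dosed women who have no later efficacy assessment

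*Protocol*

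**What the plan says.** Section 7.4, the harms analysis plan, opens: "Using intention to treat analysis, the absolute risk, the frequency/incident rate and severity grade of anticipated adverse drug reactions". The same sentence extends this to serious adverse reactions and SUSARs, reported per study arm. The section does not mention a Safety set.

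Section 9.3 defines the analysis populations. Its ITT set is "all randomized patients with at least one relevant post-baseline efficacy assessment, and who had at least one dose of study drug", and "patients will be analyzed according to the treatment they were assigned to at randomization". Its Safety set is "all patients that received at least one dose of study drug and had at least one post-baseline safety assessment", and "Patients will be analyzed according to treatment received". Section 9.3 is the only place where the protocol defines ITT as a population, and no section links either set to the harms analysis in 7.4.

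On timing, Section 4.9 schedules "Hemoglobin concentration with the Hemocue haemoglobinometer at screening, two and six weeks and six months postpartum". Section 4.10.3 and Table 3 add a hemoglobin check at 12 weeks. For infusion reactions, Section 7.3.1.1 states: "Patients should be closely monitored for signs of hypersensitivity during and for at least 30 min after administration".

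**The concern.** Safety and tolerability are part of the trial's first aim (Section 2.1), and adverse drug events are a listed secondary outcome (Section 3.1.2). For that outcome the protocol gives two incompatible rules: one set is grouped by assignment and depends on an efficacy measurement; the other is grouped by receipt and depends on a safety assessment.

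The efficacy condition matters because of when events occur. The infusion is given once, within about two days of delivery, and its acute reactions are watched for in the minutes that follow. The first scheduled efficacy measurement is at two weeks. Using the 9.3 ITT set for harms therefore makes inclusion depend on something that happens after the event of interest and that the event may influence. A woman who dies before any efficacy measurement cannot enter that set.

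**Working it through.** **1. The sets side by side (Section 9.3)**

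| | ITT set | Safety set |
|---|---|---|
| Dose received | required | required |
| Condition after baseline | a relevant efficacy assessment | a safety assessment |
| Grouping | as assigned | as received |

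The difference in membership is dosed women with a safety assessment but no efficacy assessment. The difference in grouping is women given the other arm's drug; Section 11.1 lists incorrect treatment as an example of a violation.

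**2. Who falls out of the ITT set**

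- A woman who stops study drug because of a reaction is not excluded by that alone. Section 6.5 keeps her in follow-up to six months with all assessments, and one later hemoglobin is enough.
- A woman who dies, withdraws consent or is lost before any efficacy assessment is excluded. The glossary says no further assessments are planned after premature withdrawal.

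**3. Effect on the reported risk**

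There is no stated figure to reproduce, and the documents give no reaction rate, so the following is an assumed range.

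Inputs: 700 women in the intravenous arm (Section 4.3); *r*, assumed true risk of an early serious reaction; *s*, assumed share of women with such a reaction who have no later efficacy assessment; *m*, assumed share of other women who have none.

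Risk in the ITT set = 700·r·(1−s) / [700·(1−r)·(1−m) + 700·r·(1−s)]

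If every infused woman is in the Safety set, the risk there is *r*.

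With r = 0.5% (3.5 expected events), m = 10%, s = 50%: the numerator is 3.5 × 0.5 = 1.75, the denominator is 696.5 × 0.9 + 1.75 = 628.6, and the risk is 0.28%.

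| r | m | s = 0 | s = 25% | s = 50% | s = 100% |
|---|---|---|---|---|---|
| 0.50% | 5% | 0.53% | 0.40% | 0.26% | 0% |
| 0.50% | 10% | 0.56% | 0.42% | 0.28% | 0% |
| 1.00% | 5% | 1.05% | 0.79% | 0.53% | 0% |
| 1.00% | 10% | 1.11% | 0.83% | 0.56% | 0% |

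When s = m the factor (1−m) cancels and the ITT-set risk equals *r*. With r = 0.5% and s = m = 10%, it is 3.15 / (626.85 + 3.15) = 3.15/630 = 0.50%. So the ITT set understates the risk when s > m and slightly overstates it when s < m.

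The 10% is borrowed from the loss allowance in Section 4.3, which concerns the six-week outcome. It is not an estimate of the share of women with no assessment at any later visit.

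**4. The Safety set's own condition**

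Section 9.3 does not define a safety assessment. Infused women are observed for at least 30 minutes after dosing (Section 4.6.1), which could count as one. Oral-arm women take tablets home, and their next scheduled symptom check is at two weeks. The condition can therefore remove women unequally between the arms.

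**The case against.** The strongest reply is that intention to treat in 7.4 may mean only grouping as randomized. Section 7.4 does not cite 9.3, and 9.4 speaks of the principle rather than the set. On that reading the efficacy condition disappears. This is a fair reading, but it leaves the conflict in grouping with the Safety set, and an analyst who looks for a definition of ITT finds only the restricted one. A statistical analysis plan may map outcomes to sets, but here the protocol itself states both rules.

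A reader might infer two stronger claims. The first is that women with early serious reactions generally drop out of the harms result. The documents do not support this: any one later efficacy assessment keeps a woman in, Section 6.5 continues follow-up after drug is stopped, Section 4.10.6 requires a home visit within 48 hours of a missed appointment, and Section 5.3 requires repeated contact attempts. The second is that the bias certainly favors the intravenous arm. It runs that way only if s > m, and nothing in the documents gives either share.

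Two further points stand in part. Maternal and infant deaths are separate secondary outcomes counted from enrolment (Section 3.1.2), and serious events are reported to the oversight bodies whatever the analysis set (Section 7.2.6). Neither settles which women form the denominator in the harms analysis. On grouping, nothing suggests much crossover between a supervised infusion and tablets, so that effect may be small.

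**Conclusion.** The contradiction is in the text: 7.4 and 9.3 imply different memberships and different grouping for the same harms, and the protocol does not reconcile them. The exclusion is conditional. It arises if the 9.3 ITT set is used, and it affects only dosed women who die, withdraw consent or are lost before any efficacy assessment, including any who had an early infusion reaction. The intravenous-arm risk is understated if such reactions go with a higher chance of having no later assessment. The size cannot be taken from the documents; the table above is a range under assumed inputs and not an estimate. Because safety is a stated aim and the remedy is only wording, it should be corrected.

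**What to change.** - **Section 7.4:** replace the intention-to-treat wording with the Safety set, grouped by treatment received, as the population for adverse reactions, serious adverse reactions and SUSARs.
- **Section 9.3:** define the Safety set as every woman who received any study drug, with no assessment after baseline required. Failing that, state that observation after dosing and any reported event count as a safety assessment.
- **Deaths:** state that maternal and infant deaths are counted from enrolment among all randomized women, by assigned arm.

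The cost is a wording amendment to the analysis sections. It needs no new data collection and does not change the sample size.

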- p) Incidence of post-natal maternal death from enrolment up to six weeks and at six months postpartum.
- q) Incidence of adverse drug events.
- r) Quality of life measured using the WHOQOL BREF at enrollment, six weeks, and six months post-partum.

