7 ADVERSE EVENTS AND REPORTING REQUIREMENTS

7.1 Adverse Events

- An adverse event (AE) is the appearance or worsening of any undesirable sign, symptom, or medical condition occurring after starting the study drug even if the event is not considered to be related to study drug. Study drugs include the investigational drug/ control drug under evaluation that is given during the treatment phase of the study.
- Medical conditions/diseases present before starting study drug are only considered adverse events if they worsen after starting study drug.
- Abnormal laboratory values or test results constitute adverse events only if they induce clinical signs or symptoms, or are considered clinically significant, or require therapy. E.g., hypophosphatemia requiring treatment.
- Clinical signs and symptoms will be assessed at baseline, before dosing and at all follow-up visits, and recorded in the e-CRF. Any symptom that worsens or starts after baseline will be recorded as a new adverse event on the e-CRF.
- The occurrence of adverse events, such as fever, weakness, chills/rigors, headache, myalgia, dizziness, epigastric pain, abdominal pain, anorexia, nausea, vomiting, diarrhea, palpitations, insomnia, pruritus, coughing, tinnitus, abnormal gait, tremor, clonus, or dyskinesia, will be sought by the investigator (or designee) at each study visit and recorded in the e-CRF.
- Adverse events also may be detected when they are volunteered by the patient during or between visits or through physical examination, laboratory test, or other assessments.

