7.2 Reporting Adverse Events (AEs)

- All adverse events that occur from the point of enrollment and throughout study duration will be collected non-systematically from each participant. Participants will be routinely asked at every study visit "do you have any symptoms now or noticed any since your last visit?"
- If a participant reports an AE at enrollment but before the administration of study intervention, the AE will be reported as not related to study drug. All other adverse events reported after enrollment into the study and until the end of study will be defined and graded for severity using the National Cancer Institute Common Terminology Criteria for Adverse Events version 5.0
- Study site coordinators/clinician will document on the appropriate study e-CRF, and clinical case notes all AEs reported by or observed in enrolled study participants regardless of severity and presumed relationship to study product.
- The study clinician must provide on the AE e-form information on symptoms, time of onset, severity, frequency, product-relatedness, actions taken and participant outcome.
- The causality of AE to trial drugs will be determined by the principal investigator and documented along with the interventions given, and the outcome.
- The PI may request additional information from the site if it is needed to further evaluate the AE.

- Site coordinators will report serious adverse events (SAEs; see section 7.2.5) to the principal Investigator and the local Ethics committee as soon as possible and in accordance with the local ethics committee requirements.
- Discontinuation of study drug may be considered if a participant experiences a severe adverse drug event of Grade 3 or higher. Decision for discontinuation will be made by the PI and or the study participant. Study personnel will document the circumstances and data leading to discontinuation.

All adverse events must be recorded on the e-CRF with the following information:

- 1. Event (nomenclature/description) (See section 7.2.1)
- 2. The severity grade (mild, moderate, severe, life threatening or death) (see section 7.2.2)
- 3. Its relationship to the study drug(s) (see section 7.2.3)
- 4. Its duration (start and end dates or if continuing at final physical exam)
- 5. Whether it constitutes a serious adverse event (SAE)
- 6. Action taken (Treatment)
- 7. Outcome

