7.2.3 Relationship of AE to study product

The Chief Investigator or designated Principal Investigator must determine the relationship of the AE to the product under investigation and document in the appropriate section of the e-CRF. For each AE, an assessment of the relatedness to the study drugs should be made using the following scale:

- **Unrelated:** Onset of the AE had no reasonable temporal relationship to administration of the study product or a causal relationship to administration of the study product is biologically implausible or the event is attributed to an alternative etiology.
- **Unlikely-related**: Onset of the AE has an inconceivable possibility that the event was related to, or caused by the investigational intervention?
- **Possibly related:** Onset of the AE has a reasonable temporal relationship to study product administration and a causal relationship is not biologically implausible.
- **Probably related:** Onset of the AE has a strong temporal relationship to administration of the study product that cannot be explained by the participant's clinical state or other factors and a causal relationship is not biologically implausible.
- **Definitely related:** Onset of the AE shows a distinct temporal relationship to administration of the study product that cannot be explained by the participant's clinical state or other factors, or the AE occurs on re-challenge, or the AE is a known reaction to the product or chemical group or can be predicted by the product's pharmacology.
- These criteria in addition to good clinical judgement should be used as a guide for determining the causal assessment. If it is felt that the event is not related to study drug therapy, then an alternative explanation should be provided.

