7.3 Safety

Adverse events will be monitored throughout the study to assess the general safety and tolerability of the two treatment groups.

Safety assessments will consist of:

- monitoring and recording all adverse events
- the monitoring of laboratory tests results
- regular measurement of vital signs
- physical examinations as indicated.

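### Section 7.4 states a by-arm harm analysis only for anticipated reactions and for serious events attributed to the drug; it states none for all serious adverse events or for unanticipated adverse events

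*Protocol*

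**What the plan says.** Section 7.4 of the protocol is the data analysis plan for harm. It names four things:

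- how often anticipated reactions to the drugs occur in each arm and how severe they are, with gastrointestinal symptoms, low blood pressure and low phosphate among the examples;
- "the incident rate of any Serious Adverse Reactions (SAR) which are SAEs that are thought to be causally linked to the trial drug";
- the unexpected part of that group: "Suspected Unexpected Serious Adverse Reaction (SUSAR) which are unexpected occurrence of a SAR for each arm of the study will be collated and analyzed";
- a summary of serum phosphate.

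Section 9.4, the general analysis plan, adds no adverse-event analysis. The matching secondary outcome, 3.1.2 (q), reads "Incidence of adverse drug events".

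Collection is wider. Section 7.1 defines an adverse event as one "occurring after starting the study drug even if the event is not considered to be related to study drug", and section 7.2 has sites document "all AEs reported by or observed in enrolled study participants regardless of severity and presumed relationship to study product". Section 7.3 gives the purpose of monitoring as "to assess the general safety and tolerability of the two treatment groups".

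On attribution, section 7.2.3 states: "The Chief Investigator or designated Principal Investigator must determine the relationship of the AE to the product under investigation". Section 4.5 says that the trial is open label and that the research nurse who completes the adverse event form is blinded. It mentions no blinding of the person who judges causality.

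**The concern.** The randomised comparison of harm is the comparison of all events by arm. Once serious events are kept only if someone attributes them to the drug, membership of the analysed set becomes a judgement made after randomisation, and here that judgement can depend on the arm. The scale in 7.2.3 asks about timing relative to administration and whether the event is a known reaction to the product, so it can hardly be applied without knowing the product. The two regimens also give different scope for a temporal link: one infusion at enrolment against tablets twice daily until six weeks.

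At stake is whether the trial can support its aim of comparing safety and tolerability. Suppose one arm had more hospital admissions or life-threatening illnesses of a kind that nobody linked to iron. The analysis in 7.4 would not show the excess unless those events also fell under one of the named secondary outcomes. The same holds for an unanticipated non-serious symptom.

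**Working it through.** **1. Collected events set against stated by-arm analyses (Protocol sections 3.1.2, 7.1, 7.2, 7.2.5, 7.2.6, 7.4, 9.4)**

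| Event | Collected? | By-arm analysis stated? |
|---|---|---|
| Anticipated reaction | Yes | Yes, 7.4 |
| Hypophosphatemia | Yes | Yes, 7.4 and outcome (l) |
| SAE judged causally linked | Yes | Yes, 7.4 (SAR) |
| Unexpected SAE judged causally linked | Yes | Yes, 7.4 (SUSAR) |
| Maternal, neonatal or infant death, any cause | Yes | Yes, outcomes (m) to (p) |
| Transfusion to 6 weeks, secondary postpartum haemorrhage to 12 weeks, maternal infection to 6 weeks | Yes | Yes, outcomes (f), (h), (k) |
| Other SAE not attributed (for example hospitalisation, life-threatening event or disability from another cause) | Yes | None stated |
| Unanticipated non-serious AE | Yes | None stated |

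The last two rows are the gap. SUSARs do not close it, because 7.2.6 requires such an event to be serious and also to have a reasonable possibility of a causal link.

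**2. How far the filter reaches.** The causality condition is explicit for SARs, and so for SUSARs. It is not explicit for the anticipated reactions, which can be read as event types counted by arm. Nor is it explicit for outcome (q), since no section says whether an adverse drug event needs a case-by-case verdict on causality.

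**3. What the filter does to a comparison.** Let p be the all-cause SAE risk in an arm and a the share of SAEs attributed to the drug. The analysed risk is p × a, so

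analysed risk ratio = (p_FCM / p_FS) × (a_FCM / a_FS).

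With no true difference, p_FCM = p_FS and the ratio is a_FCM / a_FS, whatever the event rate. Under assumed shares of 40% and 50% it is 0.40 / 0.50 = 0.80. Under assumed shares of 30% and 60% it is 0.30 / 0.60 = 0.50.

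**4. Would this produce a false significant result?** The protocol gives neither p nor a. As an assumption, take an SAE risk of 1% to 3% in both arms and 700 × 0.90 = 630 women per arm (section 4.3: 700 per arm, 10% loss).

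| Assumed SAE risk, both arms | Expected SARs at 30% vs 60% | Fisher p < 0.05 | Expected SARs at 40% vs 50% | Fisher p < 0.05 |
|---|---|---|---|---|
| 1% | 630 × 0.003 = 1.9 vs 630 × 0.006 = 3.8 | 4% | 2.5 vs 3.2 | 1% |
| 2% | 3.8 vs 7.6 | 12% | 5.0 vs 6.3 | 3% |
| 3% | 5.7 vs 11.3 | 21% | 7.6 vs 9.5 | 4% |

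At rates of this order the estimate shifts, but a spurious significant finding is uncommon unless attribution differs strongly. The other effect is loss of information: in the 2% row with 30% attribution, 12.6 − 3.8 = 8.8 of the 12.6 expected SAEs in that arm fall outside the SAR count.

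**The case against.** The strongest reply has four parts.

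- **The gravest events are already compared without a filter.** This stands. A reader might infer from 7.4 that unattributed serious events are never compared between the arms, or carry no weight. Section 3.1.2 does not support that: a maternal or infant death, a transfusion, a secondary haemorrhage or a maternal infection within the stated window counts whatever its cause.
- **Attribution is explicit only for serious reactions.** This also stands. A reader might infer a high rate of false safety findings by applying unequal attribution to common symptoms. That needs an assumed high event rate, assumed shares and a filter that 7.4 does not plainly place on those symptoms. The wording that introduces examples of anticipated reactions leaves that list open, though only among anticipated ones.
- **Other review exists.** Section 10.1 has the DSMB review the prevalence of serious adverse events with no relatedness limit, and section 9.3 defines a safety population analysed by treatment received. Neither is a stated by-arm final analysis of all SAEs. The safety population comes with no list of events.
- **A statistical analysis plan may add all-cause tables.** It may, and 7.4 does not say that its list is exclusive. But 7.4 goes beyond leaving detail open: for serious events it names the attributed subset as what is analysed.

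That the causality assessors know the allocation is an inference from the open-label design and the content of the scale. The protocol does not say so. The blinding of the nurse in section 4.5 concerns data collection.

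**Conclusion.** The concern holds in a limited form. The stated harm analysis covers anticipated reactions and attributed serious reactions. Outside deaths, transfusion, secondary postpartum haemorrhage and maternal infection, no by-arm analysis is stated for all SAEs or for unanticipated AEs, although the data are collected. The serious-reaction comparison therefore rests on a causality judgement by the Chief or Principal Investigator, with no blinded adjudication described.

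The gap follows from reading the sections together and needs no assumed figure. Its numerical effect cannot be derived from the protocol. The risk ratios of 0.80 and 0.50 and the significance rates shown in the working rest wholly on assumed SAE risks and attribution shares; they illustrate the mechanism and predict nothing about this trial. The point does not affect the primary outcome. It should be corrected because the correction is cheap and the protocol claims to compare general safety.

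**What to change.** In section 7.4, add three comparisons by arm regardless of attribution: any SAE, any AE of Grade 3 or higher, and any AE. Report each as the number and proportion of women with at least one event, with a risk difference and 95% confidence interval. Add a table of all event terms by arm. Keep SARs, SUSARs and drug-related events as secondary descriptions. In outcome (q), state that events are counted whatever the attribution.

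The cost is a few lines of protocol or analysis-plan wording and some extra tables. No new data, visits or change in clinical management are needed. All-cause rates will look higher than drug-related rates, which the report should explain.
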